- b. Screening will consist of 2 CRU outpatient visits (S1 and S2) between 3 to 14 days apart, with the first screening visit occurring within 28 days prior to investigational product administration (Day 1). The second screening visit is only to demonstrate stable renal function with difference between eGFRs at S1 and S2 required to be $\leq 25\%$ of the value obtained at S1. If participant meets all screening criteria at S2 visit, and Day -1 visit can be performed immediately, the participant may be admitted to the unit at conclusion of S2 visit. Other screening procedures completed during S1 do not need to be repeated. See [Section 4.1](#) for outpatient visit screening schedule.
- c. Contact may occur via telephone contact and must occur 28 to 35 days from the last administration of ritonavir or from the time of early termination/discontinuation. If participant demonstrates an increase of $>25\%$ in serum creatinine from Day -1 to Day of discharge, he or she will be asked for a follow-up visit to collect eGFR.
- d. Demographics will include race, age, and gender.
- e. Complete physical examination at screening (normal renal function; Cohort 3 is at screening only only), Day -1, Day 3, and early termination. Brief physical examination at any time point as deemed necessary by the investigator.
- f. Height to be obtained at S1 only, weight to be obtained at S1, S2 and Day -1.
- g. Only when the participant demonstrates an increase of $>25\%$ in serum creatinine from Day -1 to Day of discharge. Only serum creatinine and weight information will be collected for eGFR assessment.
- h. Safety laboratory assessments include chemistry, hematology, and urinalysis (and microscopy, if needed) and will be performed at Screening, Day -1, Day 3, and early termination day. All the assessments must be collected following at least a 4 hour fast.

Visit Identifier ^a	Screening ^b		Day -1 ^b	Day 1	Day 2	Day 3	Follow-up Contact	Early Termination/Discontinuation (DC)
	Day -28 to Day -2							
Days Relative to Day 1	S1	S2						28-35 Days ^c

i. Only serum creatinine will be assessed on S2 for eGFR assessment.

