4. STUDY DESIGN

4.1. Overall Design

This is a Phase 1, non-randomized, open-label, 2-part study to investigate the effect of renal impairment on the plasma and urine (if applicable) PK, safety and tolerability of a single oral dose of PF-07321332 in combination with the PK boosting agent ritonavir in approximately

36 participants. Part 1 will be conducted in approximately 24 adult male and female participants with stable mild or moderate renal impairment and a control group of participants with normal renal function. Part 2 will be conducted in approximately 8 adult male and female participants with stable severe renal impairment. A staged approach, as outlined in detail below, will be followed in the study.

Participants will be selected and categorized into normal renal function or renal impairment groups based on their eGFR as shown in Table 1.

Table 1. Renal Function Categories by eGFR Ranges

Cohort	Renal Impairment ^a	Estimated eGFR ^b (mL/min)	Number of Participants
1	Moderate Renal Impairment	≥30 to <60	8
2	Mild Renal Impairment	60 – <90	8
3	None (Normal)	≥90	8 (up to 12)
4	Severe Renal Impairment	<30 and not requiring dialysis	8

- a. Stages of renal impairment are based on Kidney Disease Outcomes Quality Initiative (KDOQI) Clinical Practice Guidelines for Chronic Kidney Disease (CKD).⁵
- b. Estimate of eGFR based on CKD-EPI formula. The average of the 2 screening eGFR value will be used for group assignment.

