Note that the value of eGFR, which is directly obtained from the laboratory or calculated using the equation above, is generally normalized to an average body size of 1.73 m² for diagnosis, prognosis and treatment of renal disease. In terms of clearance of renally filtered drugs (including secreted drugs), renal elimination capacity is related to absolute GFR in mL/min. To use the CKD-EPI-derived, BSA-adjusted value of eGFR to obtain absolute GFR (mL/min) for renal disease classification or participant assignment into different renal disease groups, this value should be multiplied by the individual participant's BSA (ie, measured BSA/1.73 m²). The BSA of an individual can be calculated by the following formula as described below:

$$\text{BSA} = (\text{Weight}^{0.425} \times \text{Height}^{0.725}) \times 0.007184$$

In summary, GFR in mL/min calculated as below will be used for renal impairment group placement:

Step 1: Obtain the CKD-EPI-derived eGFR:

Step 2: Convert the CKD-EPI-derived, BSA-adjusted eGFR obtained above to absolute GFR (mL/min) for eligibility assessment using the following equation:

- eGFR (mL/min) = eGFR (mL/min/1.73m²) × participant's BSA, where BSA is calculated as $\text{BSA} = (\text{Weight}^{0.425} \times \text{Height}^{0.725}) \times 0.007184$.

CL_{CR} will also be estimated from a spot serum creatinine measurement using the following C-G equation:

$$\text{CL}_{\text{CR}} (\text{mL/min}) = \frac{(\text{140} - \text{age [years]}) \times \text{total body weight (kg)} \times (0.85 \text{ for females})}{72 \times \text{serum creatinine (mg/dL)}}$$

Note that eGFR calculated by the CKD-EPI equation will be used for categorization of degrees of renal impairment. Nevertheless, renal function will be estimated using both C-G and CKD-EPI equations in this study and dose recommendations will be made using both C-G and CKD-EPI equations.

To be enrolled into the study, participant must demonstrate stable renal function, with $\leq 25\%$ change based upon screening S1 eGFR and screening S2 eGFR (calculated by the CKD-EPI equation). The S2 eGFR assessment should be performed between 3 to 14 days

after the S1 eGFR assessment. The average of these 2 eGFR values will be used for group placement based on the renal function classification category.

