Each enrolled participant will receive a single 100 mg dose of PF-07321332 administered orally in combination with the PK boosting agent ritonavir administered as a 100 mg dose at -12, 0, 12, and 24 hours relative to PF-07321332 dosing.

The total planned duration of participation, from the Screening visit to the last Follow-up phone call, is approximately up to 9 weeks.

Calculation of eGFR

The following CKD-EPI equation will be used to calculate eGFR ($S_{cr, std}$ denotes serum creatinine measured with a standardized assay for serum creatinine):

If female and SCr is ≤ 0.7 mg/dL:

$$eGFR (\text{mL/min}/1.73 \text{ m}^2) = 144 \times (S_{Cr, \text{std}}/0.7)^{-0.329} \times 0.993^{\text{age}} (\times 1.159, \text{ if Black})$$

If female and SCr is > 0.7 mg/dL:

$$eGFR (\text{mL/min}/1.73 \text{ m}^2) = 144 \times (S_{Cr, \text{std}}/0.7)^{-1.209} \times 0.993^{\text{age}} (\times 1.159, \text{ if Black})$$

If male and SCr is ≤ 0.9 mg/dL:

$$eGFR (\text{mL/min}/1.73 \text{ m}^2) = 141 \times (S_{Cr, \text{std}}/0.9)^{-0.411} \times 0.993^{\text{age}} (\times 1.159, \text{ if Black})$$

If male and SCr is > 0.9 mg/dL:

$$GFR (\text{mL/min}/1.73 \text{ m}^2) = 141 \times (S_{Cr, \text{std}}/0.9)^{-1.209} \times 0.993^{\text{age}} (\times 1.159, \text{ if Black})$$

Note that the value of eGFR, which is directly obtained from the laboratory or calculated using the equation above, is generally normalized to an average body size of 1.73 m^2 for diagnosis, prognosis and treatment of renal disease. In terms of clearance of renally filtered drugs (including secreted drugs), renal elimination capacity is related to absolute GFR in mL/min. To use the CKD-EPI-derived, BSA-adjusted value of eGFR to obtain absolute GFR (mL/min) for renal disease classification or participant assignment into different renal disease groups, this value should be multiplied by the individual participant's BSA (ie, measured BSA/ 1.73 m^2). The BSA of an individual can be calculated by the following formula as described below:

$$BSA = (Weight^{0.425} \times Height^{0.725}) \times 0.007184$$

In summary, GFR in mL/min calculated as below will be used for renal impairment group placement:

Step 1: Obtain the CKD-EPI-derived eGFR:

Step 2: Convert the CKD-EPI-derived, BSA-adjusted eGFR obtained above to absolute GFR (mL/min) for eligibility assessment using the following equation:

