- $eGFR (\text{mL/min}) = eGFR (\text{mL/min}/1.73 \text{ m}^2) \times \text{participant's BSA}$, where BSA is calculated as $BSA = (Weight^{0.425} \times Height^{0.725}) \times 0.007184$.

CL_{CR} will also be estimated from a spot serum creatinine measurement using the following C-G equation:

$$CL_{CR} (\text{mL/min}) = \frac{(140 - \text{age [years]}) \times \text{total body weight (kg)} \times (0.85 \text{ for females})}{72 \times \text{serum creatinine (mg/dL)}}$$

Note that eGFR calculated by the CKD-EPI equation will be used for categorization of degrees of renal impairment. Nevertheless, renal function will be estimated using both C-G and CKD-EPI equations in this study and dose recommendations will be made using both C-G and CKD-EPI equations.

To be enrolled into the study, participant must demonstrate stable renal function, with $\leq 25\%$ change based upon screening S1 eGFR and screening S2 eGFR (calculated by the CKD-EPI equation). The S2 eGFR assessment should be performed between 3 to 14 days after the S1 eGFR assessment. The average of these 2 eGFR values will be used for group placement based on the renal function classification category.

- If the renal function stability criterion is met and the renal function classification category remains the same between S1 eGFR and the average of the S1 and S2 eGFRs, participant will be eligible for enrollment.
- If the renal function stability criterion is not met, participant will be screen failed.
- If the renal function stability criterion is met but the renal function classification category changes between S1 eGFR and the average of the S1 and S2 eGFRs, the eGFR measurement at Day -1 will also be used to determine the appropriate group classification category using an average of all 3 eGFR values, to determine whether the participant will be eligible for enrollment.

Please see Table 2 below regarding demonstration of stable renal function:

Table 2. Criteria to Establish Stable Renal Function

Renal function Measurement	eGFR (mL/min)	Criterion for stability
S1	G1	N/A
S2 (Within 3 to 14 days after S1)	G2	$D = G2 - G1 \times 100/G1^a$ If $D \leq 25\%$; stable If $D > 25\%$; not stable

a. Parenthesis of $| |$ represents absolute values.

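### Step 2 of the eGFR conversion, the equation named for cohort placement, does not print the division by 1.73 that the note above it gives; the same conflict is in the protocol and the SAP

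*Protocol*

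**What the plan says.** Protocol section 4.1, under Calculation of eGFR, first gives CKD-EPI equations that return eGFR in mL/min/1.73 m². A note then explains that drug elimination relates to absolute GFR, so the indexed value must be converted before participants are assigned to groups: "this value should be multiplied by the individual participant's BSA (ie, measured BSA/1.73 m²").

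A two-step summary follows. Step 1 obtains the CKD-EPI value. Step 2, which the protocol says is for eligibility assessment, is "eGFR (mL/min) = eGFR (mL/min/1.73m²) × participant's BSA, where BSA is calculated as" weight^0.425 × height^0.725 × 0.007184. The figure 1.73 appears in Step 2 only inside the unit label of the indexed eGFR.

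SAP section 2.1 repeats both the note and Step 2 and is equally explicit about their use: "GFR in mL/min calculated as below will be used for renal impairment group placement".

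The cut-offs applied to the result are in mL/min (protocol Table 1 and sections 5.1.2 and 5.1.3): "Participants will be selected and categorized into normal renal function or renal impairment groups based on their eGFR as shown in Table 1". The same section requires a C-G estimate and states that "dose recommendations will be made using both C-G and CKD-EPI equations".

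**The concern.** Two adjacent statements of one conversion give different numbers, and the one without the divisor is the one designated for use. An equation that may be programmed into a screening worksheet should return the intended value when the numbers are put in.

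Weight is scheduled for this purpose. For the follow-up eGFR, schedule of activities footnote g says "Only serum creatinine and weight information will be collected for eGFR assessment", and the indexed CKD-EPI equation has no weight term.

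Cohort is the only factor in the primary ANOVA (SAP Appendix 1). The moderate-to-normal AUCinf ratio, compared with 1.5, decides whether Cohort 2 is enrolled (protocol 4.1) and whether urine is assayed (protocol 8.4.2). If Step 2 were entered literally, that ratio would describe a different range of renal function from the one in Table 1. The CKD-EPI and C-G values behind the dose recommendations would also be on different scales.

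**Working it through.** **Inputs.** The CKD-EPI, BSA and C-G equations and both conversions are from protocol 4.1; the cut-offs of 30, 60 and 90 mL/min are from Table 1. The BSA formula prints no units. Kilograms and centimetres are assumed, since height in metres gives a BSA of about 0.07 for an 80 kg, 1.75 m person. The participants below are illustrative, non-Black, and within the eligibility limits (BMI 17.5 to 40 kg/m², weight above 50 kg). The documents give no figure to reproduce.

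**Ratio of the two conversions.**
- Note: G_note = eGFR_indexed × BSA / 1.73
- Step 2 as printed: G_step2 = eGFR_indexed × BSA
- G_step2 / G_note = 1.73, whatever the BSA.

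**Effective cut-offs on the note's scale under literal entry.** 30/1.73 = 17.3; 60/1.73 = 34.7; 90/1.73 = 52.0 mL/min. The moderate label would cover 17.3 to 34.7, and the mild label 34.7 to 52.0, which lies wholly inside Table 1's moderate range.

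**One case in full.** Man, 60 years, 70 kg, 170 cm, creatinine 1.8 mg/dL:
- Indexed eGFR = 141 × (1.8/0.9)^-1.209 × 0.993^60 = 141 × 0.4326 × 0.6561 = 40.0
- BSA = 70^0.425 × 170^0.725 × 0.007184 = 1.81 m²
- Note: 40.02 × 1.8097 / 1.73 = 41.9 mL/min, moderate
- Step 2: 40.02 × 1.8097 = 72.4 mL/min, mild
- C-G: (140 − 60) × 70 / (72 × 1.8) = 43.2 mL/min

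**Further cases (mL/min).**

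| Participant | BMI | Note | Step 2 as printed | C-G |
|---|---|---|---|---|
| Man 60 y, 70 kg, 170 cm, creatinine 1.8 | 24.2 | 41.9 moderate | 72.4 mild | 43.2 |
| Woman 65 y, 65 kg, 160 cm, 2.3 | 25.4 | 21.0 severe | 36.3 moderate | 25.0 |
| Man 55 y, 80 kg, 175 cm, 1.3 | 26.1 | 69.5 mild | 120.2 normal on eGFR alone | 72.6 |
| Man 55 y, 80 kg, 175 cm, 0.9 | 26.1 | 108.3 normal | 187.4 normal | 104.9 |
| Woman 40 y, 100 kg, 160 cm, 2.5 | 39.1 | 27.2 severe | 47.0 moderate | 47.2 |
| Man 50 y, 120 kg, 175 cm, 2.5 | 39.2 | 38.8 moderate | 67.1 mild | 60.0 |

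Not every participant changes category; the fourth does not.

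**Would the plan's own checks catch it?**
- Stability rule: |1.73·G2 − 1.73·G1| / (1.73·G1) = |G2 − G1| / G1. The factor cancels, so the 25% rule is unaffected and gives no warning.
- C-G: in the four cases with BMI 24 to 26, the note's value is 0.84 to 1.03 times C-G and the printed value 1.45 to 1.79 times, so a discrepancy would show. C-G uses total body weight, however. In the two cases with BMI about 39 it lies nearer the printed value (47.0 against 47.2; 67.1 against 60.0) than the note's. The documents also prescribe no comparison of C-G with CKD-EPI before placement.

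**The case against.** The strongest reply is that the intended conversion is already on the page. The note's parenthesis tells the reader that the BSA multiplier means measured BSA over 1.73, and Step 2 is introduced as a summary a few lines later. Step 2 is also dimensionally sound: a quantity in mL/min per 1.73 m², multiplied by BSA in m², gives mL/min only if the 1.73 is carried through as a divisor. On that view this is untidy notation.

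Most of that stands. The intent is recoverable, and the matter is a conflict between two adjacent statements, not an unknown rule. But Step 2 redefines BSA within its own line by the height-weight formula, so someone working from the equation alone has no instruction to divide. The SAP repeats the conflict. Text extraction is an unlikely cause, since both documents show the same form of Step 2 and both keep the divisor in the note.

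A reader might go further and infer that participants were misclassified, or try to count how many of each cohort of 8 would be. The documents support neither. Nothing shows that literal entry occurred. A headcount would also need a distribution of GFR within each band, which is not given, and would have to assume that Cohort 2 opens, which is conditional. Cohort 3's health criteria (protocol 5.1.2 and 5.2.2) further limit who could be labelled normal.

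A reader might equally infer that the required C-G value is an adequate safeguard. The high-BMI cases show that it is not.

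**Conclusion.** The point holds as a drafting conflict in an operative equation, present in both documents. Its size is exact but conditional: if Step 2 is entered as printed, absolute GFR is 1.73 times the note's value for every participant, and the 30/60/90 cut-offs act as 17.3/34.7/52.0 mL/min. That factor does not depend on the assumed body sizes; the worked cases do, and serve only to show that a category can change. No actual misclassification is shown or claimed.

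No claim is made about the regression of PK parameters on eGFR either. The effect there would depend on which eGFR value is entered and on what the trt term in the SAP code stands for. The conflict deserves correction because the equation determines the only factor in the primary model, and neither the stability rule nor C-G reliably reveals the error.

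**What to change.** In protocol 4.1 and SAP 2.1, print Step 2 as: eGFR (mL/min) = eGFR (mL/min/1.73 m²) × (participant's BSA / 1.73). Use the same conversion wherever absolute Day -1 eGFR enters the PK analysis.

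For anyone already screened, recompute indexed eGFR × BSA / 1.73 from the recorded creatinine, age, sex, race, height and weight, and compare it with the value used for placement. Do not use C-G for this check: at high BMI it can agree with the wrong value and flag the right one. Screen-failure records stay at the site as source (protocol 5.4), so that part of the check has to be done there.

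The cost is one line in each document and a recalculation from values already collected; no new data are needed.

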4.2. Scientific Rationale for Study Design

This study is a Phase 1, non-randomized, open-label study of PF-07321332 in participants with mild and moderate renal impairment and participants with normal renal impairment, matched for age, body weight and, to the extent possible, for gender composition (Part 1), and in participants with severe renal impairment (Part 2). Details on age and body weight matching criteria are specified in [Section 4.1](#).

PF-07321332 alone is thought to be primarily eliminated through a CYP450 mediated oxidation with CYP3A4 as the major contributor ($f_m = 0.99$) and renal excretion as unchanged a minor component. However, in the presence of the CYP3A4 inhibitor ritonavir, preliminary data suggests renal excretion may play a significant role in PF-07321332

excretion. Based on preliminary population PK modeling, mild renal impairment is predicted to have a minor impact on exposure of PF-07321332 (<15% increase in C_{max} and AUC). Therefore, the effect of renal impairment on PF-07321332 PK will be initially evaluated in moderate renal impairment, the renally impaired population more likely to be of impact. If the study results demonstrate that moderate renal impairment does not alter PK to an extent that warrants dosage adjustment (See [Section 4.1, Criteria to enroll Cohort 2](#)), mild renal impairment will not be evaluated. If the results do not support such a conclusion, enrollment will open to mild renal impairment. The decision to conduct Part 2, in participants with severe renal impairment, will also be based on results from moderate renal impairment participants from Part 1. More specifically, if data from Part 1 supports the use of population PK modelling to predict drug exposures in participants with severe renal impairment, the study may stop after Part 1.

A single dose of PF-07321332 was selected and is considered appropriate as available data do not indicate PF-07321332 PK are time-dependent, and hence, single dose data are considered predictive of steady state. As ritonavir is not eliminated renally, multiple doses of 100 mg ritonavir will be administered at -12, 0, 12, and 24 hours relative to PF-07321332 dosing to ensure adequate PK boosting effect over the duration of PF-07321332 exposure.

PF-07321332 is not extensively bound to human plasma proteins, with f_u of 0.31 observed in the in vitro protein binding study. Thus, no additional blood samples will be collected in this study for ex vivo protein binding analysis.

4.2.1. Choice of Contraception/Barrier Requirements

Human reproductive safety data are limited for PF-07321332, but there is no suspicion of human teratogenicity based on the intended pharmacology of the compound. Therefore, the use of a highly effective method of contraception is required (see [Appendix 4](#)).

4.2.2. Collection of Retained Research Samples

Retained Research Samples will be collected and stored for further analyses which may, for example, provide greater understanding of the study intervention.

4.3. Justification for Dose

A single oral dose of 100 mg PF-07321332, pharmacokinetically enhanced with ritonavir (100 mg at -12, 0, 12, and 24 hours relative to PF-07321332), is planned in this study. This is anticipated to be at the lower end of the clinically effective dose range, and below the anticipated Phase 2/3 dose of PF-07321332/ritonavir of 300/100 mg. Although single doses up to 750 mg PF-07321332 with ritonavir have been evaluated, exposure increased less than dose proportional within the 250 mg to 750 mg dose range evaluated. Therefore, 100 mg PF-07321332 is appropriate considering systemic exposures of PF-07321332 may be increased in the presence of renal impairment.

When co-administered with ritonavir, doses of PF-07321332 up to 750 mg single dose and 500 mg q12h for 10 days were generally safe and well tolerated based on preliminary data

form the Phase 1 study C4671001. There have been no deaths or serious adverse events or SUSARs reported. Based on review of preliminary (unaudited) data, all reported adverse events have been of mild intensity. There were no clinically meaningful findings in vital signs, ECG, or potential Hy's Law cases reported during the study.

Doses may be modified in Part 2 based on emerging safety, tolerability, and PK data.

The dose of ritonavir to be used in this study is 100 mg administered q12h. This dose is the typical dose of ritonavir when dosed as a PK enhancer. As ritonavir is not eliminated renally, and is not expected to be significantly altered by renal impairment, no dose reduction is considered necessary.

4.4. End of Study Definition

The end of the study is defined as the date of last scheduled procedure shown in the [SoA](#) for the last participant in the trial.

A participant is considered to have completed the study if he/she has completed all parts of the study, including the last scheduled procedure shown in the [SoA](#).

5. STUDY POPULATION

This study can fulfill its objectives only if appropriate participants are enrolled. The following eligibility criteria are designed to select participants for whom participation in the study is considered appropriate. All relevant medical and nonmedical conditions should be taken into consideration when deciding whether a particular participant is suitable for this protocol.

Prospective approval of protocol deviations to recruitment and enrollment criteria, also known as protocol waivers or exemptions, is not permitted.

